6.3.2 Treatment interruption and treatment discontinuation

Patients who permanently discontinue study drug before completing the study should be scheduled for a visit as soon as possible, at which time all of the assessments listed for the final visit will be performed. The Study Treatment Completion eCRF should be completed, documenting the date and reason for stopping randomized study treatment. Any safety finding that leads to discontinuation of study drug should be captured on the AE eCRF.

[figure not shown]
All patients who discontinue study drug, including those who refuse to return for a final visit, will be contacted by the investigational site for safety evaluations during the 30 days following the last dose of study drug.

Patients who discontinue study drug should be considered withdrawn from the study after the final visit assessments are performed or when it is clear that the patient will not return for these assessments.

All patients must be followed for AEs and SAEs for 30 days after the last dose of study treatment. Patients lost to follow up should be recorded as such on the eCRF. For patients who are lost to follow-up, the investigator should show “due diligence” by documenting in the source documents steps taken to contact the patient, e.g., dates of telephone calls, registered letters, etc.

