6.3.3 Follow-up for toxicities

Patients whose treatment is interrupted or permanently discontinued due to an AE or abnormal laboratory value must be followed at least once a week for 4 weeks, and subsequently at 4-week intervals, until resolution or stabilization of the event, whichever comes first.

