7.1.3.1 Criteria for premature patient withdrawal

Patients may voluntarily withdraw from the study or be dropped from it at the discretion of the investigator at any time.

Premature patient withdrawal refers to the point/time when the patient exits from the study prior to the planned completion of all study treatment administration and/or assessments; at this time, all study drug treatment is discontinued and no further assessments are planned.

Patients who become pregnant, withdrew consent, or died must be withdrawn from the study.

Patients may be withdrawn from the study if any of the following occur:

- Unwillingness to comply with procedures as outlined in the study protocol, including unwillingness to comply with the prescribed study treatment
- Discovery of failure of randomization
- Discovery of patient ineligibility
- Intake of prohibited medications
- Adverse event(s)
- Abnormal lab value(s)
- Unsatisfactory therapeutic effect
- Protocol violation
- Lost to follow-up
- Administrative problems

Patients must be withdrawn from the study anytime when transfusion as rescue therapy is needed to ensure that all medically indicated transfusion requirements are covered, regardless of participation in the study.

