6. Whether it is serious, where a serious adverse event (SAE) is defined as in [Section 8.2.1](#)

All adverse events should be treated appropriately. If a concomitant medication or non-drug therapy is given, this action should be recorded on the Adverse Event CRF.

Once an adverse event is detected, it should be followed until its resolution or until it is judged to be permanent, and assessment should be made at each visit (or more frequently, if necessary) of any changes in severity, the suspected relationship to the study treatment, the interventions required to treat it, and the outcome.

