4.3 Data handling conventions

Partial dates will be listed as partial dates. For computing time/duration, the following rules will be used to impute partial dates: if the day and month is missing, it will be replaced by 30th of June (to be used only for prior events, e.g., medical history), if only the day is missing it will be replaced by 15th of that month. For dates known to be within the trial period, if this imputation makes the date later than trial completion date, then the trial completion date will be used; if the imputed date is earlier than the first medication date, then the first medication date will be used. The same rules of assigning AE start and end dates will apply for study medication start and end dates for subjects with missing or partial date of or with duplicate records of study medication.

Partially or completely missing AE onset dates and concomitant medication dates are imputed according to the standard Novartis imputation rules as described in the following:

Date imputation is the creation of a new, complete date from a partial one according to an agreed and acceptable algorithm. Missing date for AE will be handled according to STL standard.

A partial date is simply an incomplete date e.g.,
ddOCT2001 the days are missing from this DDMMYYYY date

Partial AEs start dates, if left partial, would ultimately mean the following

- It would not be possible to place the AE in time.
- Therefore the treatment/dosage at the time of the event would be unknown.
- Therefore the event could not be reported/summarized appropriately – if at all.

Therefore it is important to perform date imputation to ensure that as many data events are represented as correctly as possible. Of course partial and/or missing dates should *also* be caught as edit checks and passed back to the investigator for resolution.

There **will be no** attempt to impute the following:

- **Missing** AE start dates
- AE start dates **missing the year**
- Partial/missing AE **end dates**

Table 4-2 explains the abbreviations used.

Table 4-2 AE/Treatment Date Abbreviations

	Day	Month	Year
Partial Adverse Event Start Date	<not used>	AEM	AEY
Treatment Start Date (TRTSTD)	<not used>	TRTM	TRTY

Table 4-3 describes the possible combinations and their associated imputations. In the light grey boxes the upper text indicates the imputation and the lower text the relationship of the AE start date to the treatment start date (TRTSTD).

Table 4-3 Imputation algorithm

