	AEM MISSING	AEM < TRTM	AEM = TRTM	AEM > TRTM
AEY MISSING	NC Uncertain	NC Uncertain	NC Uncertain	NC Uncertain
AEY < TRTY	(D) Before TRTSTD	(C) Before TRTSTD	(C) Before TRTSTD	(C) Before TRTSTD
AEY = TRTY	(B) Uncertain	(C) Before TRTSTD	(B) Uncertain	(A) After TRTSTD
AEY > TRTY	(E) After TRTSTD	(A) After TRTSTD	(A) After TRTSTD	(A) After TRTSTD

The legend to the above table is shown in Table 4-4.

Table 4-4 Relationship and Imputation Legend

Relationship	
Before TRTSTD	Indicates AE start date prior to Treatment Start Date
After TRTSTD	Indicates AE start date after Treatment Start Date
Uncertain	Insufficient to determine the relationship of AE start date to Treatment Start Date
Imputation Calculation	
NC / Blank	No convention/imputation
(A)	01MONYYYY
(B)	TRTSTD+1
(C)	15MONYYYY
(D)	01JULYYYY
(E)	01JANYYYY

Few examples are shown in Table 4-5.

Table 4-5 Example Scenarios

Partial AE start date	Treatment start date	Relationship	Imputation Calculation	Imputed Date
12mmyyyy	20OCT2001	Uncertain	NC	<blank>
ddmmm2000	20OCT2001	Before	(D)	01JUL2000
ddmmm2002	20OCT2001	After	(E)	01JAN2002
ddmmm2001	20OCT2001	Uncertain	(B)	21OCT2001
ddSEP2001	20OCT2001	Before	(C)	15SEP2001
ddOCT2001	20OCT2001	Uncertain	(B)	21OCT2001
ddNOV2001	20OCT2001	After	(A)	01NOV2001

For any continuing events (e.g. AEs, concomitant medication, etc) which needs to be summarized for annual reports (or any interim analyses), when a date cut-off date is used an indication in the listings will be done to inform that the event is continuing. For patients who discontinue the study with ongoing events, the discontinuation date will be used as the completion date of the event.

Vital sign, Study Completion, CMP, ECG and laboratory assessment dates will be imputed in associating visit date from Visit-based event date imputation (AVIS) (see RAP Module 8).

Any event which has a partial date and requires imputing but has no specific imputation rule will be described in the RAP Module 8 and the imputed will be as follows:

- If the day and month is missing, it will be replaced by 1st of July. If only the day is missing it will be replaced by the 1st of that month. Partial dates will remain partial in the data listings.
- Missing day information for start date of prior chelation therapy or start date of history of blood transfusions will be imputed by the 15th of the Month. If the month will be missing it will be imputed by July.

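### SAP 4.3 gives adverse events still ongoing at study discontinuation an end date, against its own no-imputation rule; the protocol's passages on follow-up after stopping also need reconciling

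*SAP*

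**What the plan says.** **End dates in the SAP.** Section 4.3 (Data handling conventions) contains three statements that bear on an AE without an end date.

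- A list introduced by "There will be no attempt to impute the following" includes "Partial/missing AE end dates".
- For continuing events at a data cut-off (annual reports or interim analyses), "an indication in the listings will be done to inform that the event is continuing".
- The next sentence reads: "For patients who discontinue the study with ongoing events, the discontinuation date will be used as the completion date of the event".

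**AE record in the protocol.** Section 8.1.1 has the investigator record either start and end dates or that the event is ongoing at the end of the study.

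**Follow-up after stopping.**

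- Protocol 6.3.3, on treatment interrupted or stopped because of a laboratory abnormality or AE: such patients "must be followed at least once a week for 4 weeks, and subsequently at 4-week intervals, until resolution or stabilization of the event". The earlier of those two outcomes ends this follow-up.
- Protocol 8.1.1: once an AE is detected, "it should be followed until its resolution or until it is judged to be permanent". Section 8.1.2.1 has laboratory abnormalities that qualify as AEs followed until they are normal or adequately explained.
- Protocol 6.3.2: "Patients who discontinue study drug should be considered withdrawn from the study after the final visit assessments are performed", or once it is clear the patient will not return. Section 7.1.3 says the same.
- Protocol 7.1.3.1: at premature withdrawal, "all study drug treatment is discontinued and no further assessments are planned".
- Protocol Table 7-1: the 30-day safety follow-up (Visit 501) schedules adverse events only, with no laboratory tests.

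**Week-12 rule.** Under Protocol 4.1 and Table 4-1, an Hb rise below 1 g/dL with Hb below 12 g/dL removes a combination-arm patient from the study. An EPO-arm patient with the same result switches to the combination and stays.

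**The concern.** An event known to be unresolved when the patient leaves has no end date. Giving it one makes a listing read as if the event had stopped that day, and shortens any duration computed from it. Safety of the combination is a secondary objective. Whether creatinine or transaminase rises, rash and cytopenias resolve after deferasirox (DFX) is stopped is a question readers will bring to the listings.

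There are two further risks. The compulsory week-12 exit exists in one arm only, so artificial end dates could be more common there. And if the protocol can be read as ending assessments at the final visit, the data that would show whether an event resolved may not be collected.

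**Working it through.** No figure in the plan needs reproducing; the check is mainly textual.

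**1. Can the SAP sentences be obeyed together?** Take an AE recorded as ongoing in a patient who discontinues. Its end date is empty. The no-imputation list says to leave it empty; the completion-date sentence says to fill it. The cut-off sentence shows the intended handling of a truly continuing event, which is to flag it, but applies this only to annual reports and interim analyses. The SAP does not separate an end date that is missing because the event is ongoing from one missing for other reasons.

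**2. What date is used?** The discontinuation date is not defined. SAP 2.6.1 distinguishes an EOT page (777) from an end-of-study page (778). Protocol 4.2 and SAP 4.2.6 count withdrawal as including the 30-day follow-up, whereas Protocol 6.3.2 and 7.1.3 place it after the final visit. Illustration, with assumed onset on Day 70 and true length 8 weeks (56 days), in a patient leaving at Day 84 (nominal Visit 10 in SAP Table 4-1):

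- closed at Day 84: 84 − 70 + 1 = 15 days
- closed at Day 84 + 30 = Day 114: 114 − 70 + 1 = 45 days
- patient still in the study to Day 168: 56 days

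In the first two cases the recorded end is false. SAP 2.10.1 also counts AEs as on-treatment up to 30 days after the last dose. If the date means the final visit, an AE starting after that visit would receive an end date before its onset.

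**3. Which outputs change?** SAP 2.10.2 and 2.10.2.1 plan incidence by system organ class and preferred term, severity and relationship, plus seriousness and action-taken tables. None uses an AE end date, and neither document specifies an AE duration, outcome or time-to-resolution table. The effect is on listings and any derived duration.

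**4. Is the effect unequal between arms?** The upper eligible baseline Hb, with the 5% tolerance, is 10 × 1.05 = 10.5 g/dL. A rise below 1 g/dL leaves Hb below 11.5 g/dL, so the second condition (Hb below 12) does not limit the exit. Let d be background discontinuation, assumed equal in both arms, and q the share of remaining combination patients who leave at week 12 by rule. The documents give neither. With 60/2 = 30 per arm:

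- combination discontinuing = d + (1 − d)q; EPO = d
- combination share of discontinuations = [d + (1 − d)q] / [2d + (1 − d)q]

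| d | q | Combination | EPO | Combination share |
|---|---|---|---|---|
| 5% | 60% | 18.6 | 1.5 | 93% |
| 10% | 40% | 13.8 | 3.0 | 82% |
| 30% | 10% | 11.1 | 9.0 | 55% |

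The direction follows from the design if d is equal. The size spans 55% to 93% over d = 5–30% and q = 10–60%, and could shrink or reverse if the EPO arm loses more patients for other reasons. These are counts of patients who discontinue, not of patients with an ongoing AE.

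**5. Follow-up passages side by side.** The 30-day contact is worded as a minimum, so it can coexist with longer follow-up of a known event. What cannot be squared is a patient counted as withdrawn after the final visit with nothing further planned (6.3.2, 7.1.3, 7.1.3.1), and the same patient followed until the event resolves, stabilizes, normalises or is judged permanent (6.3.3, 8.1.1, 8.1.2.1). Table 7-1 schedules no laboratory test after EOT with which to show that a laboratory event has resolved.

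**The case against.** The strongest reply is that nothing planned is affected: the AE tables count incidence, and an end date changes no count. That stands, and it limits the point to listings and derived durations. The record also keeps its ongoing status, and nothing says the derived date overwrites it; programming details are in RAP Module 8, which is not available here. This too is fair, but the SAP sentence as written still puts an end date beside an event known not to have ended. For creatinine, transaminases and blood counts, the laboratory listings and shift tables show the course up to EOT independently of AE dates. That is correct for the period on study, but not for the time after EOT.

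On follow-up, much of the text can be read together: 30 days as a minimum for everyone, 6.3.3 as the specific rule for stops due to an AE or laboratory value, 8.1.1 for any detected AE. Table 7-1 lists scheduled visits, so the absence of event-driven ones is weak evidence alone. The residual conflict with the withdrawal wording remains.

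A reader might infer more than the documents support:

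- That the safety tables will understate AEs on the combination. They will not; the counts are unchanged.
- That the false end dates fall mainly in the combination arm by a known amount. The Hb-rise distribution and background dropout are not given.
- That events leading to stopping and patients leaving for Hb non-response are one group. Section 6.3.3 covers the first, and the second only if treatment was also stopped or interrupted for an AE or laboratory value.
- That 8.1.1 sets a weekly schedule. It does not; only 6.3.3 does, and it allows stabilization as an endpoint.

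**Conclusion.** The point holds in a limited form. SAP 4.3 is internally inconsistent on AE end dates and departs from the ongoing status that Protocol 8.1.1 provides for. Following the completion-date sentence would place false end dates in listings and any derived duration; incidence, severity and relationship tables are unaffected. The one-sided week-12 exit makes an unequal effect between arms possible. Its direction rests on equal background discontinuation, and its size cannot be derived. The 55% to 93% range illustrates assumed inputs and is not an estimate. The 15- and 45-day figures depend on an undefined date and concern a statistic the plan does not commit to report.

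The protocol conflict is real but narrow: withdrawal after the final visit with no further assessments, against follow-up to an outcome.

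**What to change.** In SAP 4.3, replace the completion-date sentence with one rule: an event not ended at last contact is reported as ongoing/not recovered with no end date, and any duration is censored at last contact. Define the discontinuation date explicitly (EOT, page 777, or study evaluation completion, page 778) wherever the SAP uses it. This is a wording change with a matching programming specification. Its cost is that some durations are shown as incomplete.

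In the protocol, reconcile 6.3.2, 7.1.3, 7.1.3.1 and Table 7-1 with 6.3.3, 8.1.1 and 8.1.2.1, so that a site can tell what is assessed and recorded after a patient stops. Which schedule applies is for the sponsor and investigators to settle. That part needs a protocol clarification; its operational cost depends on the schedule they adopt.

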4.4 Protocol deviations

The complete list of PDs, which is usually described in a Novartis VAP Module 3, is described in the following tables:

Table 4-6 CSR Reportable Protocol Deviation Categories

Violation Code	Protocol ID	Description of CSR Reportable Category
Inclusion Criteria	Ixx	Subject enrolled despite selection criteria not being met
Exclusion Criteria	Exx	Subject enrolled despite selection criteria not being met
Withdrawal	Dxx	Subject developed withdrawal criteria during the study but was not withdrawn
Treatment	Sxx	Subject received the wrong treatment or incorrect dose
Prohibited Medication	Mxx	Subject took an excluded concomitant medication
Other	Gxx	For deviations which jeopardize the safety or rights of the individual trial subjects, or jeopardize the scientific value of the trial may be reported under this category, should it not align with any of the 4 categories. Protocol deviations captured under this category should be reviewed during a PD meeting for CSR- Reportable validity and must be reported in CSR if appropriate.

The table below specifies the actions to be taken if any of the deviations listed in the VAP occur:

Table 4-7 Protocol Deviations List

Deviation Code	Protocol Deviation description	Action taken
I01	Patient has not provided consent prior to study start	Report as PD, include in FAS and Safety Set.
I24	Written informed consent not provided at all	Report as PD, Exclude from all analyses.
I25	Patient signed incorrect version of informed consent	Report as PD, include in FAS and Safety Set.
I02	Subject is < 18 years or age missing	Report as PD, include in FAS and Safety Set.
I03	Patient does not suffer from MDS	Report as PD, include in FAS and Safety Set.
I04	MDS is not lasting ≥ 3 months or < 3 years	Report as PD, include in FAS and Safety Set.
I05	MDS is secondary to treatment with radiotherapy, chemotherapy, and/or immunotherapy for malignant or autoimmune disease	Report as PD, include in FAS and Safety Set.
I06	Patient has no low- and Int-1- risk MDS	Report as PD, include in FAS and Safety Set.
I07	Hemoglobin is ≥ 10.5 g/dL at Screening Visit 1 and/or Screening Visit 2	Report as PD, include in FAS and Safety Set.
I08	Hemoglobin is < 7.6 g/dL at Screening Visit 1 and/or Screening Visit 2	Report as PD, include in FAS and Safety Set.
I09	Patient has history of ≥ 10 times RBC transfusions in total	Report as PD, include in FAS and Safety Set.
I27	Patient has history of ≥ 10 units of RBC transfusions in total	Report as PD, include in FAS and Safety Set.
I10	ANC < 500/mm ³ at Screening Visit 1 and/or Screening Visit 2	Report as PD, include in FAS and Safety Set.
I11	Platelet count < 30,000/mm ³ at Screening Visit 1 and/or Screening Visit 2	Report as PD, include in FAS and Safety Set.
I12	Serum creatinine > 1.5 times ULN in mean value of measurements at Screening Visit 1 and Screening Visit 2	Report as PD, include in FAS and Safety Set.
I13	Patients with creatinine clearance < 40 mL/min.	Report as PD, include in FAS and Safety Set.

I20	Creatinine clearance below the concentration limit locally approved PI at Screening Visit 1 and/or Screening Visit 2	Report as PD, include in FAS and Safety Set.
I14	AST and ALT > 2.0 times ULN at Screening Visit 1 and/or Screening Visit 2	Report as PD, include in FAS and Safety Set.
I15	Serum total bilirubin \geq 3.0 mg/dL at Screening Visit 1 and/or Screening Visit 2	Report as PD, include in FAS and Safety Set.
I16	FE/TIBC (TSAT) < 20% at Screening Visit 1	Report as PD, include in FAS and Safety Set.
I17	SF is \leq 270 ng/mL at Screening Visit 1 and/or Screening Visit 2	Report as PD, include in FAS and Safety Set.
I18	SF is \geq 1650 ng/mL at Screening Visit 1 and/or Screening Visit 2	Report as PD, include in FAS and Safety Set.
I19	SF is \geq 1100 ng/mL at Screening Visit 1 and/or Screening Visit 2	Report as PD, include in FAS and Safety Set.
I21	Endogenous EPO levels \geq 500 units/L at Screening Visit 1	Report as PD, include in FAS and Safety Set.
I22	Patient received cytotoxic chemotherapeutic agents or experimental agents for treatment of MDS within 8 weeks prior Screening	Report as PD, include in FAS and Safety Set.
I23	Patient is transfusion dependent (> 2U RBC/4 weeks at any time during the last 12 weeks period prior to study entry)	Report as PD, include in FAS and Safety Set.
I26	Patient is transfusion dependent (\geq 2U RBC/month during the past 3 months)	Report as PD, include in FAS and Safety Set.
E01	Patient has MDS with isolated del(5q)	Report as PD, include in FAS and Safety Set.
E02	Prior EPO treatment or other recombinant growth factors with reported outcome, for \geq 4 weeks or within 3 month before Screening	Report as PD, include in FAS and Safety Set.
E03	Patient receiving steroids or immunosuppressive therapy for the improvement of hematological parameters	Report as PD, include in FAS and Safety Set.
E04	B12 or folate deficiency with or without clinical symptoms	Report as PD, include in FAS and Safety Set.

E05	Uncontrolled seizures	Report as PD, include in FAS and Safety Set.
E06	Uncontrolled hypertension	Report as PD, include in FAS and Safety Set.
E07	History of other malignancies and has not been confirmed disease free for ≥ 3 years	Report as PD, include in FAS and Safety Set.
E08	Significant medical condition interfering with the ability to partake in this study	Report as PD, include in FAS and Safety Set.
E09	Thromboembolic event within the past 3 years	Report as a PD, include in FAS and Safety Set.
E10	Known allergic reaction to EPO or human serum albumin	Report as PD, include in FAS and Safety Set.
E11	Clinical or laboratory evidence of active Hepatitis B or Hepatitis C (HBsAg in the absence of HBsAb OR HCV Ab positive with HCV RNA positive)	Report as PD, include in FAS and Safety Set.
E12	Patient has known HIV-1 seropositivity	Report as PD, include in FAS and Safety Set.
E13	Clinically significant anemia resulting from iron deficiencies, autoimmune or hereditary hemolysis, or gastrointestinal bleeding	Report as PD, include in FAS and Safety Set.
E14	Active bleeding	Report as PD, include in FAS and Safety Set.
E15	Patient is pregnant or nursing	Report as PD, include in FAS and Safety Set.
E16	Female of childbearing potential with missing serum HCG test	Report as PD, include in FAS and Safety Set.
E17	Patient with child-bearing potential without adequate birth control	Report as PD, include in FAS and Safety Set.
E19	Hepatic impairment fulfilling criteria of Child-Pugh Class B or C	Report as PD, include in FAS and Safety Set.
G04	Blood Sample for Hematology not collected for analysis at the required visit	Report as PD, include in FAS and Safety Set.
S01	Patient not exposed to study medication	Report as PD, include in FAS and Safety Set.
S02	Epo dose is not stopped as per protocol for more than 1 week but Hb increase is ≥ 1 g/dL and total Hb ≥ 12 g/dL in period week 1-24	Report as PD, include in FAS and Safety set.

S19	Epo dose is stopped for more than 1 week but Hb increase is not ≥ 1 g/dL and total Hb not ≥ 12 g/dL in period week 1-12	Report as PD, include in FAS and Safety Set.
S20	Epo dose is stopped for more than 1 week but Hb increase is not ≥ 1 g/dL and total Hb not ≥ 12 g/dL in period week 13-24	Reported as PD, include in FAS and Safety Set.
S21	Epo dose reduced below assigned dose as per protocol for more than 1 week in period week 1-12	Report as PD, include in FAS and Safety Set.
S22	Epo dose reduced below assigned dose as per protocol for more than 1 week in period week 13-24	Report as PD, include in FAS and Safety Set.
S23	Epo dose increased above assigned dose as per protocol for more than 1 week in period week 1-12	Report as PD, include in FAS and Safety Set.
S24	Epo dose increased above assigned dose as per protocol for more than 1 week in period week 13-24	Report as PD, include in FAS and Safety Set
S03	Epo dose maintained at 40.000 units/week and not increased to 60.000 units/week after 4 weeks as per protocol for more than 1 week but Hb increase < 1 g/dL and total Hb < 12 g/dL	Report as PD, include in FAS and Safety Set.
S05	Epo dose increased to 60.000 units/week and not maintained at 40.000 units/week after 4 weeks as per protocol for more than 1 week but Hb increase ≥ 1 g/dL and total Hb < 12 g/dL	Report as PD, include in FAS and Safety Set.
S06	Patient randomized to monotherapy not switched to combination therapy as per protocol or switch delayed for more than 1 week after 12 weeks of treatment but Hb increase < 1 g/dL and total Hb < 12 g/dL	Report as PD, include in FAS and Safety Set.
D12	Patient randomized to combination therapy not discontinued after 12 weeks of treatment as per protocol or discontinuation delayed for more than 1 week but Hb increase < 1 g/dL and total Hb < 12 g/dL	Report as PD, include in FAS and Safety Set.
S10	Patient randomized to combination therapy stopped DFX treatment for more than 1 week in period week 1-12 not as per protocol	Report as PD, include in FAS and Safety Set.
S25	Patient assigned to combination therapy stopped DFX treatment for more than 1 week in period week 13-24 not as per protocol	Reported as PD, include in FAS and Safety Set.
M01	Forbidden concomitant medication as per	Report as PD,

	protocol	include in FAS and Safety Set.
M02	Patient received iron chelation therapy other than the study treatment	Report as PD, include in FAS and Safety Set.
D01	Transfusion during the study but not withdrawn	Report as PD, include in FAS and Safety Set.
D02	Pregnancy during the study, but not withdrawn	Report as PD, include in FAS and Safety Set.
S11	Patient randomized but received wrong study drug	Report as PD, include in FAS and Safety Set.
D03	≥50% decrement from maximum response levels in granulocytes or platelets but patient not withdrawn	Report as PD, include in FAS and Safety Set.
D04	Reduction of Hb level ≥1.5g/dL compared to best response but patient not withdrawn	Report as PD, include in FAS and Safety Set.
D05	Consent withdrawn but patient not withdrawn	Report as PD, Exclude from all analyses.
S12	Deferasirox dose was not reduced despite serum creatinine increase of ≥33% above baseline and above ULN at 2 consecutive occasions	Report as PD, include in FAS and Safety Set.
S13	Deferasirox treatment was not interrupted despite severe case of skin rash	Reported as PD, include in FAS and Safety Set.
S14	Deferasirox treatment was not interrupted despite persistent and progressive increase in serum transaminase levels that cannot attributed to other causes	Report as PD, include in FAS and Safety Set.
S15	Deferasirox treatment was not interrupted despite unexplained cytopenia	Report as PD, include in FAS and Safety Set.
S16	Deferasirox dose not recalculated despite > 10% change in body weight	Report as PD, include in FAS and Safety Set.
S17	Deferasirox treatment was not interrupted despite severe hypersensitivity reactions	Reported as PD, include in FAS and Safety Set.
S18	Deferasirox treatment was not permanently discontinued despite suspected Stevens Johnson syndrome	Report as PD, include in FAS and Safety Set.
G01	Use of local laboratory instead of central laboratory	Report as PD, include in FAS and Safety Set.
G03	Patient was randomized with missing central lab results and/or based on local lab results	Reported as PD, include in FAS and Safety Set.

The RAP module 8 will include variables that will flag the missing values at baseline for the laboratory parameters or flag corresponding to certain assessments which leads to the exclusion of the patient from any analyses.

